Electronic Alerts for Acute Kidney Injury Amelioration (ELAIA-1)
NCT Title and ID: Optimizing Electronic Alerts for Acute Kidney Injury
NCT02753751
April 24, 2020

SECTION V: RESEARCH PLAN

1. **Statement of Purpose:** State the scientific aim(s) of the study, or the hypotheses to be tested.

This study is designed to determine whether automated, electronic alerts for Acute Kidney Injury (AKI) will be effective at reducing progression of AKI, inpatient dialysis, and inpatient mortality rates in a hospitalized population.

2. **Background:** Describe the background information that led to the plan for this project. Provide references to support the expectation of obtaining useful scientific data.

Acute kidney injury (AKI) carries a significant, independent risk of mortality among hospitalized patients^{1,2}. Recent studies have demonstrated increased mortality among patients with even small increases in serum creatinine concentration^{3,4}. International guidelines for the treatment of AKI focus on appropriate management of drug dosing, avoiding nephrotoxic exposures, and careful attention to fluid and electrolyte balance⁵. Early nephrologist involvement may also improve outcomes in AKI⁶. Without appropriate provider recognition of AKI, however, none of these measures can be taken, and patient outcomes may suffer. AKI is frequently overlooked by clinicians⁷, but carries a substantial cost, morbidity and mortality burden.

Our research group conducted a pilot, randomized trial of electronic alerts for acute kidney injury in 2014.⁸ The trial, which randomized 2400 patients with AKI as defined by an increase in creatinine of 0.3mg/dl over 48 hours or 50% over 7 days, found that alerting physicians to the presence of AKI did not improve the course of acute kidney injury, reduce dialysis or death rates. Our pilot study demonstrates that there is clinical equipoise regarding the effectiveness of alerting, and that alerting to the presence of this condition (which does not have a treatment) is not standard of care.

Our pilot study was conducted in a single hospital, and the alert itself did not describe specific actions that a provider could take. In the present proposal, we seek to expand upon our prior study to determine if the use of an electronic alert will improve best practices for the care of hospitalized patients with AKI and/or improve rates of progression of AKI, dialysis or mortality in hospitalized patients across multiple hospital centers.

We propose a randomized, controlled trial of an electronic AKI alert system. Using the Kidney Disease: Improving Global Outcomes (KDIGO) creatinine criteria, inpatients at six hospitals, including Yale New Haven Hospital, YNH – St. Raphael Campus, and Bridgeport hospital, will be randomized to usual care versus an electronic alert informing providers of the presence of AKI and providing them with an AKI order set for management of AKI. The form of the electronic alerts (including the information contained in the alert) is described in detail in the research plan. The primary outcome will be a composite of progression of acute kidney injury, dialysis and death within 14 days of randomization. Secondary outcomes would focus on the efficient delivery of care and include length of stay, ICU utilization, rate of acute dialysis, 30-day readmission rate, and a variety of process of care variables.

[figure not shown]
3. **Research Plan:** Summarize the study design and research procedures using non-technical language that can be readily understood by someone outside the discipline. **Be sure to distinguish between standard of care vs. research procedures when applicable, and**

include any flowcharts of visits specifying their individual times and lengths. Describe the setting in which the research will take place.

General Design

This is a randomized, single-blind intervention trial of an electronic alert coupled to an AKI order set versus standard care among patients with AKI.

Study Flow Diagram:

Subject participation will be limited to the duration of hospitalization.

Subject Selection and Withdrawal

Inclusion Criteria

1. Adults ≥ 18 years admitted to a participating hospital.
2. Acute kidney injury as defined by KDIGO creatinine criteria
 - 0.3mg/dl increase in inpatient serum creatinine over 48 hours OR
 - 50% relative increase in inpatient serum creatinine over 168 hours.

Exclusion Criteria

1. Dialysis order prior to AKI onset
2. Initial creatinine ≥ 4.0 mg/dl
3. Prior admission in which patient was randomized
4. Admission to hospice service or comfort measures only order
5. ESKD diagnosis code
6. Kidney transplant within six months

Subject Recruitment and Screening

Due to the nature of this research, subjects will be recruited when electronically identified by the presence of a rising serum creatinine concentration as defined by the inclusion criteria.

Identification of subjects will be performed within the EPIC system, using a best-practice alert build developed by the Joint Data Analytics Team (JDAT) at Yale. The build will examine the most recent creatinine value, and compare it to the minimum value in the past 48 hours and 7 days. If the current value is 0.3mg/dl above the 48-hour minimum, or 50% higher than the 7-day minimum, the patient is defined as having AKI and he or she will be randomized as part of this trial. We have secured enthusiastic agreements from both JDAT and the Best Practice Alerts committee to engage in this line of research.

As this is an intervention assessing the influence of an alert system on provider behaviors surrounding AKI, we cannot inform patients of their participation in the study at the time of enrollment, as this would contaminate the randomized exposure.

While the unit of randomization is the patient, clinicians may also be considered subjects of this research. We will engage in pre-trial and periodic outreach to all clinicians who may be exposed to this study, informing them of the nature of the study, the fact that it is a randomized trial, and that alerts do not fire for all patients with AKI. We will additionally inform them that limited data is being collected regarding provider behavior. However, we will also make it clear that data subject to clinician behavior (such as AKI documentation) will NOT be linked to individual clinicians. All such data will only be analyzed in aggregate.

Intervention

Description

Patients randomized to the intervention will have an alert generated within the electronic health record, which will consist of a “pop-up” within the EMR when the provider assesses a patient record after the AKI-defining creatinine value has been registered. Providers who receive an alert include physicians, physician assistants, nurse practitioners, advanced practice registered nurses, fellows, physician/anesthesiologists, physician/sedation specialists, and residents. These alerts will be built by JDAT, who, as mentioned, have agreed to aid in the development of this study. The alert text will be displayed as follows:

BestPractice Advisory - Zzzcreatinineone, Ericastestpatient

Patient Safety (1)

AKI Alert:

Your patient has been identified as having ACUTE KIDNEY INJURY. Relevant creatinine values over the last seven days are listed below:

Most recent: **4 mg/dl**

Lowest in past 7 days: **2 mg/dl**

Highest in past 7 days: **4 mg/dl**

THIS ALERT DOES NOT FIRE FOR ALL PATIENTS. This patient is part of a randomized trial. For more information click here: www.akistudy.org. For AKI best practices, click here: www.akistudy.org/aki-best-practices.

Open Order Set Do Not Open AKI ORDER SET Preview

Add Problem Do Not Add Acute kidney injury Edit details (Hospital problem, Share with patient)

Acknowledge Reason

Agree - Do not alert me for 48 hours Disagree with alert because...

Accept Dismiss

Intervention Duration

The AKI alert will be displayed to the relevant provider whenever the chart is opened. If the provider dismisses the alert, it will continue to “pop-up” on each subsequent opening of the patient’s medical record. The alert will stop firing for the provider under the following conditions.

- The provider acknowledges the alert by "agreeing" that AKI is present (alert will be suppressed for 48 hours)
- The most recent creatinine does not meet AKI criteria
- The patient receives an order for hemodialysis, continuous renal replacement therapy, or peritoneal dialysis
- The patient is transferred to the hospice service
- The patient is discharged from the hospital

Method for Assigning Subjects to Intervention Randomization will occur the moment AKI is detected by the electronic monitoring system within the EPIC best practice alert framework, as developed by JDAT. Randomization is achieved within the Epic system using a random number rule that is incorporated in the alert. This ensures that, upon meeting criteria, each patient is immediately and randomly assigned to an arm. Logic checks within the alerts ensure that once a patient is assigned to an arm, they remain on that arm for the remainder of their hospital stay.

Prior and Concomitant Therapy

Potential subjects will be excluded if they have a prior order for dialysis. Beyond that, all therapies are permissible within this protocol.

Blinding of Intervention

Subjects will not be informed of their randomization status or participation in this trial as the trial could not be feasibly performed if subjects were told they were enrolled. We do not feel that post-facto informing of patients randomized in this trial is appropriate for several reasons. First, there is no guideline-based specific follow-up or intervention for acute kidney injury. Second, many patients may incorrectly assume that acute kidney injury is an iatrogenic condition, caused by poor medical care, when in fact it is indicative of the severity of the underlying medical condition. Finally, most patients will not be familiar with "acute kidney injury" and informing them of the presence of the condition may engender significant stress or anxiety without offering a tangible benefit.

All investigators will be blinded to treatment assignment until the end of the trial period. Care providers will, obviously, not be blinded to the intervention as they are receiving the alert. We will engage in both pre-trial and periodic teaching and discussion with all care providers (administered through short presentations at divisional conferences) to inform clinicians about the nature of the study, the fact that alerts do not fire for all patients with AKI, and to discuss specific factors that are being measured.

Primary Study Endpoints

Primary Outcome: The primary outcome will be a composite of progression to a higher stage of acute kidney injury (a doubling or tripling of creatinine from the pre-alert baseline), inpatient dialysis, or inpatient death at within 14 days of randomization.

-For patients who are discharged, we will impute 14-day creatinine using the last observation carried forward method.

Secondary Study Endpoints

1) Mortality Outcomes

- 14-day mortality
- Inpatient mortality

2) Dialysis outcomes

- 14-day dialysis
- Inpatient dialysis
- Discharge on dialysis

3) Renal Failure Outcomes

- Percent who progress to stage 2 AKI
- Percent who progress to stage 3 AKI
- Duration of AKI

4) Readmission Rate and Costs

- 30-day readmission rate
- Cost of index hospitalization

5) Individual “Best Practice” Outcomes, proportion achieved per patient in study arm during index hospitalization

- Contrast administration
- Fluid administration
- Aminoglycoside administration
- NSAID administration / cessation
- ACE inhibitor administration / cessation
- Urinalysis order
- Documentation of AKI
- Monitoring of creatinine
- Monitoring of urine output
- Renal consult

6) Provider awareness outcomes

- Chart documentation of AKI (by post-discharge ICD-10 codes)
- Chart documentation of AKI (adjudicated)

Study Procedures

Randomization

Randomization will occur the moment AKI is detected by the electronic monitoring system within the EPIC best practice alert framework, as developed by JDAT. Beyond the primary intervention, no further tests or procedures will be performed on subjects in this trial. Randomization will be performed within the Epic system using a random number rule that is incorporated in the alert. This ensures that, upon meeting criteria, each patient is immediately and randomly assigned to an arm. Logic checks within the alerts ensure that once a patient is assigned to an arm, they remain on that arm for the remainder of their hospital stay.

Fourteen days post-randomization

Primary endpoint ascertainment

Thirty days post-randomization

Secondary endpoint ascertainment

Statistical Plan

Sample Size Determination

:

In our retrospective analysis of patients with AKI at 3 potential study hospitals, the composite outcome of death, dialysis, and progression of AKI was 24.5% (of 29,027 individuals with AKI). We believe a clinically meaningful relative reduction in this risk would be 20%, leading to an absolute rate of 19.6% in the intervention group. By enrolling 5,024 patients (2,512 in each group), we would have 90% power to detect a difference in outcome at least this extreme at a two-sided alpha of 0.05 as calculated using the Cochran-Mantel-Haenszel test (accounting for 6 hospital strata). We have elected to increase this number by 20% to account for potential contamination of the effect across

study arms, leading to a final sample size of 6,030 individuals. This sample size will also allow us to detect at least a 16% increase in best practices measures in the intervention group.

We must also consider that patients enrolled once in the trial will be excluded from enrolling again (on another admission, for example). While we don't have data on the rates of recurrent AKI we estimate that up to 20% of eligible patients may be excluded on this basis, which may slow recruitment somewhat.

In addition, pauses in trial enrollment may occur due to protocol changes / amendments based on feedback from providers and for quality improvement activities.

As such, we expect active enrollment, data acquisition, and outcome assessment to be completed over a three-year period.

Statistical Methods

The primary analysis will utilize the intention to treat principle. The primary outcome (a composite of progression of AKI, dialysis, and death) will be compared across the groups using the Mantel-Haenszel chi-square test for correction for the 6 study strata (by hospital). Statistical significance will be based on a p-value of <0.05.

In addition, a retrospective examination will be performed to assess improvement in the control group before / after intervention as a measurement of contamination. We expect that providers who receive AKI alerts on some patients may be more likely to look for AKI in other patients, potentially diluting the effect of the intervention – this pre/post intervention analysis will help in assessing that level of contamination.

Because we are enrolling patients across six sites, we will do an exploratory analysis to determine the efficacy of alerts independently at each hospital.

We have specified several subgroups in whom the benefit of an AKI alert may differ from the general population. These groups will be analyzed as secondary and exploratory analyses. They include:

- Surgical patients
- Subjects with baseline creatinine <1.0mg/dl
- Subjects with baseline creatinine <0.5 mg/dl
- Females (due to lower rate of increase in creatinine after AKI)
- African Americans (due to higher rate of increase in creatinine after AKI)
- Elderly subjects (age > 65, age > 70, and age > 75)
- Subjects in an ICU at the time of the alert
- Subjects who enter the study based on relative vs. absolute creatinine criteria vs. both

Finally, as the academic year progresses, new clinicians (such as residents and interns) may become more facile in their ability to recognize AKI, which may attenuate the effect of this intervention. We will model this in exploratory analyses using an intervention-by-time of year interaction term in models of the primary outcome.

4. Genetic Testing N/A

A. Describe

- i. the types of future research to be conducted using the materials, specifying if immortalization of cell lines, whole exome or genome sequencing, genome wide association studies, or animal studies are planned
 - ii. the plan for the collection of material or the conditions under which material will be received
 - iii. the types of information about the donor/individual contributors that will be entered into a database
 - iv. the methods to uphold confidentiality
- B. What are the conditions or procedures for sharing of materials and/or distributing for future research projects?
- C. Is widespread sharing of materials planned?
- D. When and under what conditions will materials be stripped of all identifiers?
- E. Can donor-subjects withdraw their materials at any time, and/or withdraw the identifiers that connect them to their materials?
- i. How will requests to withdraw materials be handled (e.g., material no longer identified: that is, anonymized) or material destroyed)?
- F. Describe the provisions for protection of participant privacy
- G. Describe the methods for the security of storage and sharing of materials

5. Subject Population: Provide a detailed description of the types of human subjects who will be recruited into this study.

This study will enroll individuals of greater than or equal to 18 years of age admitted to one of the 6 participating hospitals, including Yale New Haven Hospital, St. Raphael's Hospital, Greenwich Hospital, Lawrence and Memorial Hospital, Westerly Hospital and Bridgeport hospital. As Greenwich hospital, Lawrence and Memorial Hospital, Westerly Hospital and Bridgeport Hospital have their own IRBs, we will apply to each of those IRBs for approval individually. , We will enroll only patients with acute kidney injury. Exclusion and inclusion criteria are described above.

6. Subject classification: Check off all classifications of subjects that will be specifically recruited for enrollment in the research project. Will subjects who may require additional safeguards or other considerations be enrolled in the study? If so, identify the population of subjects requiring special safeguards and provide a justification for their involvement.

- | | | |
|--|------------------------------------|--|
|  Children |  Healthy |  Fetal material, placenta, or dead fetus |
|  Non-English Speaking |  Prisoners |  Economically disadvantaged persons |
|  Decisionally Impaired |  Employees |  Pregnant women and/or fetuses |

Yale Students Females of childbearing potential

NOTE: Is this research proposal designed to enroll children who are wards of the state as potential subjects? Yes No (If yes, see Instructions section VII #4 for further requirements)

7. **Inclusion/Exclusion Criteria:** What are the criteria used to determine subject inclusion or exclusion?

Inclusion Criteria

1. Adults ≥ 18 years admitted to a participating hospital.
2. Acute kidney injury as defined by KDIGO creatinine criteria
 - 0.3mg/dl increase in inpatient serum creatinine over 48 hours OR
 - 50% relative increase in inpatient serum creatinine over 168 hours.

Exclusion Criteria

1. Dialysis order prior to AKI onset
2. Initial creatinine ≥ 4.0 mg/dl
3. Prior admission in which patient was randomized
4. Admission to hospice service or comfort measures only order
5. ESKD diagnosis code
6. Kidney transplant within six months

8. How will **eligibility** be determined, and by whom?

Eligibility will be determined by a computerized algorithm. All patients admitted to YNHH, and YNHH St. Raphael Campus will be assessed electronically for eligibility (without human intervention). This assessment is performed within the Epic best practice alert framework as built with JDAT. Those that meet the inclusion criteria and who have no exclusion criteria will be automatically enrolled.

9. **Risks:** Describe the reasonably foreseeable risks, including risks to subject privacy, discomforts, or inconveniences associated with subjects participating in the research.

We consider the primary intervention (alerting of providers to the presence of a condition) to be minimal risk, however no intervention is risk free.

Risks of the generic AKI alert: Providers may be overly aggressive with diagnostic or therapeutic interventions if they are informed of the presence of Acute Kidney Injury. While we did not see this behavior in our pilot trial, we can imagine that providers who see an alert might give more fluids, or keep the patient in the hospital longer. Though, in our pilot study, there was no effect of the alert overall on rates of renal consult or dialysis, we did see a *higher* rate of renal consult and dialysis in the surgical ward subgroup, though this trend did not maintain statistical significance when adjusted for multiple comparisons.

Risks to providers: The primary risk to providers is annoyance and interruption in workflow due to the presence of alerts. Providers are, however, exposed to many alerts already in the usual flow of care. In fact, the evaluation of alerts in the clinical trial paradigm is actually vital to *reduce* the amount of alerts providers receive (by eliminating those that are ineffective).

General Risk of Alerting in the Trial Format: Not all patients with AKI will be randomized to alerting arms of this study. As such, providers may be less attentive to the presence of AKI in all patients. We mitigate this alert by including the phrase “THIS ALERT DOES NOT FIRE FOR ALL PATIENTS WITH AKI” at the end of every alert. In addition, prior to the onset of the study, our study team will engage in brief educational talks with all sections practicing in the hospitals of interest to inform them of the structure and function of the alert trial and indicate, again, that not all patients with AKI will receive an alert.

As with all studies where PHI is collected, loss of privacy is a risk for participants. We limit this risk through our use of an entirely-electronic data collection system and our data security plan outlined below.

10. Minimizing Risks: Describe the manner in which the above-mentioned risks will be minimized.

All patient data will be kept on a secure, HIPAA-compliant server with 2-factor authentication, accessible only from within the Yale firewall, or via VPN protocols, and only by study personnel. In addition, at the time of data acquisition, a unique study ID number will be assigned to each patient. All PHI will be linked to this study ID number in a database that is *separate and distinct* from the primary dataset which includes clinical information. This linking dataset will be maintained on a separate HIPAA-compliant server and will only be accessible by the study investigators.

11. Data and Safety Monitoring Plan: Include an appropriate Data and Safety Monitoring Plan (DSMP) based on the investigator’s risk assessment stated below. (Note: the HIC will make the final determination of the risk to subjects.) For more information, see the Instructions, page 24.

- a. What is the investigator’s assessment of the overall risk level for subjects participating in this study?

The protocol presents minimal risks to all subjects. If an unlikely adverse event should occur, it will be dealt with as outlined in response 11c.

- b. If children are involved, what is the investigator’s assessment of the overall risk level for the children participating in this study?

(N/A)

- c. Include an appropriate Data and Safety Monitoring Plan. Examples of DSMPs are available here <http://www.yale.edu/hrpp/forms-templates/biomedical.html>.

We have uploaded our Data and Safety Monitoring Plan with this Application.

12. **Statistical Considerations:** Describe the statistical analyses that support the study design.

Statistical Methods

The primary analysis will utilize the intention to treat principle. The primary outcome (a composite of progression of AKI, dialysis, and death) will be compared across the groups using the Mantel-Haenszel chi-square test for correction for the 6 study strata (by hospital). Statistical significance will be based on a p-value of <0.05 .

In addition, a retrospective examination will be performed to assess improvement in the control group before / after intervention as a measurement of contamination. We expect that providers who receive AKI alerts on some patients may be more likely to look for AKI in other patients, potentially diluting the effect of the intervention – this pre/post intervention analysis will help in assessing that level of contamination.

We have specified several subgroups in whom the benefit of an AKI alert may differ from the general population. These groups will be analyzed as secondary and exploratory analyses. They include:

- Surgical patients
- Subjects with baseline creatinine <1.0 mg/dl
- Subjects with baseline creatinine <0.5 mg/dl
- Females (due to lower rate of increase in creatinine after AKI)
- African Americans (due to higher rate of increase in creatinine after AKI)
- Elderly subjects (age > 65 , age > 70 , and age > 75)
- Subjects in an ICU at the time of the alert
- Subjects who enter the study based on relative vs. absolute creatinine criteria vs. both

Finally, as the academic year progresses, new clinicians (such as residents and interns) may become more facile in their ability to recognize AKI, which may attenuate the effect of this intervention. We will model this in exploratory analyses using an intervention-by-time of year interaction term in models of the primary outcome.

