alert except “dismiss”, the alert would be suppressed for 48 hours for that particular provider. If multiple providers used the EHR to care for the same patient, each of them separately received the AKI alert when they opened the patient chart. Patients randomized to the usual care group generated “silent” alerts which did not display to providers but were tracked, allowing the study team to observe which types of providers opened the chart and how often.

The alert contained an option to add AKI to the patient’s problem list, as well as a link to an AKI order set (Supplemental Figure S2); the set included options for blood and urine testing and renal imaging, but were limited to tests and procedures considered minimal risk (ie IV fluid administration was not included). Providers at each of the study hospitals received education regarding AKI and the AKI alert system prior to study rollout during departmental conferences. Educational content was standardized and included the following elements: the definition and clinical relevance of AKI, the rates of best practice completion after AKI has developed, the study design, and how to interact with the alert (specifically focusing on the consequences of “accepting” or “disagreeing” with the alert. There was no formal curriculum on how to treat AKI in various situations, but providers were reminded of best practices such as urinalysis, urine output monitoring, AKI documentation, and subsequent creatinine measurement.

The development of the alert was an iterative process which used focus groups of providers to give feedback on design elements and wording as well as incorporating suggestions from the IRB. Providers were asked what relevant information should be shown in the alert, what responses could be given, and what elements should appear in the AKI order set (although, due to IRB restrictions, no drug or fluid interventions could be included). They were also asked about alert behavior such as the appropriate “lockout” – how long the alert should be repressed after a provider interacts with it. The final alert was presented to our local Best Practice Alert committee who provided formal approval. The alert was then piloted in “silent mode” for several months for quality assurance. During this time, no

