alerts were displayed, but patient data was captured to ensure they met the inclusion / exclusion criteria and to gather data around alert frequency. Once the system was demonstrated to be working correctly, with approval from the BPA committee, the trial was started.

Outcome Measures

The primary outcome was a composite of inpatient AKI progression, receipt of dialysis, or death within 14 days of randomization. AKI progression was defined as reaching a KDIGO creatinine stage higher than the stage present at randomization. Stages 2 and 3 AKI are defined as an increase in creatinine level by 2–2.9 times and an increase ≥ 3 times baseline, respectively. Receipt of dialysis was also considered to be AKI progression. Patients discharged in the 14-day outcome period were assumed to not meet any of these outcomes had they not met them at the time of discharge. Pre-specified secondary outcomes included the components of the primary outcomes and rates of various AKI care practices. These practices included administration of contrast, fluids, or a nephrotoxic agent (an NSAID, ACE inhibitor / angiotensin receptor blocker or aminoglycoside), ordering of a urinalysis, documentation of AKI, monitoring of creatinine and urine output, and ordering for a kidney consult. An assessment of per-hospital alert effects was also pre-specified.

Data Collection

Data were collected electronically from the electronic health record using a centralized data warehouse (Joint Data Analytics Team, Yale New Haven Health System). Data collected included admission characteristics, time-updated hospital location, laboratory data, medication exposures, vital signs, comorbidities (based on ICD-10 administrative coding) and hospital disposition. Cost information was obtained from a separate database. Direct costs reflect those associated with direct patient contact involving billable services (for example lab, nursing costs, and supplies). Total costs also include non-

billable support services such as medical records, human resources, accounting, support staff, utilities and dietary costs.

Statistical Analysis

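### The best-practice endpoints are counted over the index stay with no start at randomization, which as written dilutes any alert effect on care; drug cessation is named in the protocol but not defined, and is absent from the SAP list.

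*Protocol*

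**What the plan says.** Protocol section 3, Secondary Study Endpoints, item 5, gives one window for all care-practice outcomes: "proportion achieved per patient in study arm during index hospitalization". Two of the drug items cover both giving and stopping: "NSAID administration / cessation" and "ACE inhibitor administration / cessation". No rule says who counts as exposed, from what moment, or over what period stopping is judged.

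The SAP, under Outcome Measures, calls the family "rates of various AKI care practices" and continues: "These practices included administration of contrast, fluids, or a nephrotoxic agent". It gives no window and no cessation item.

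In both documents the primary outcome is tied to the 14 days after randomization. Randomization takes place during the stay, when the algorithm detects AKI, and eligibility compares inpatient creatinine values, for example "0.3mg/dl increase in inpatient serum creatinine over 48 hours OR".

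The only planning figure for these endpoints is in Protocol section 3, Sample Size Determination: "This sample size will also allow us to detect at least a 16% increase in best practices measures in the intervention group".

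**The concern.** The care-practice endpoints show whether the alert changed what providers did. They carry weight here because improving best practice is a stated aim in the protocol's Background, and because the SAP reports unexpected harm at non-teaching hospitals and looks for an explanation in medications and renal consults, among other mediators.

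An alert cannot change care delivered before it fires. Consider a patient who has contrast, a urinalysis and an ACE inhibitor early in the stay and is randomized on day 3. Under a whole-stay count this patient scores on all three items in either arm. The more such patients there are, the closer the arms look, and a real change in practice could be read as no change.

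The drug items have a further problem. If an item means that the drug was given at any time in the stay, a patient whose NSAID or ACE inhibitor is stopped after the alert still counts as having received it.

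**Working it through.** **1. Does every patient have time at risk before randomization?** Yes. Entry needs a rise from an earlier inpatient creatinine, over 48 or 168 hours. Taken literally, the item on monitoring of creatinine is therefore met by 100% of both arms at entry.

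**2. Can the plan's own figure be reproduced?** No. The 16% increase comes without a base rate, a power or a scale (relative or absolute). It can only be bracketed. If it is relative, with 6,030 / 2 = 3,015 per arm and two-sided alpha 0.05, 90% power needs a base rate of about 22.3% or more, and 80% power about 17.7% or more.

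**3. Dilution (illustration; the rates and shares are assumptions).** Let f be the share of patients who already had the practice before randomization, equal in both arms in expectation. Let p be the probability of the practice after randomization, the same whether or not the patient had it before.

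- Whole-stay rate = f + (1 − f)p
- Whole-stay difference = (1 − f)(p₁ − p₀)
- Power = Φ{[d√n − 1.96√(2p̄(1 − p̄))] / √(p₀(1 − p₀) + p₁(1 − p₁))}, where d is the difference and p̄ the mean of the two rates

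Take p₀ = 0.25, p₁ = 0.25 × 1.16 = 0.29 and n = 3,015 per arm:

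| Count | Usual care | Alert | Difference | RR | Power |
|---|---|---|---|---|---|
| After randomization only | 25.0% | 29.0% | 4.0 points | 1.16 | 94% |
| Whole stay, f = 20% | 40.0% | 43.2% | 3.2 points | 1.08 | 71% |
| Whole stay, f = 40% | 55.0% | 57.4% | 2.4 points | 1.04 | 47% |
| Whole stay, f = 60% | 70.0% | 71.6% | 1.6 points | 1.02 | 28% |

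**4. Sensitivity to the base rate.** The same formulas with p₁ = 1.16 p₀ give, for f = 20% / 40% / 60%:

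- p₀ = 20%: power 86% after randomization, falling to 54% / 32% / 19%.
- p₀ = 30%: 98%, falling to 85% / 62% / 39%.
- p₀ = 50% (50% versus 58%): about 100%, falling to 99.9% / 98.7% / 89%. Power holds, but the RR still falls from 1.16 to 1.11 / 1.07 / 1.04.

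**5. Sensitivity to the independence assumption.** Suppose instead that 25% and 29% are shares of all patients who newly receive the practice, over and above those who already had it. The whole-stay rates are then f + 0.25 and f + 0.29, and the 4-point difference is not diluted. For f = 20% this is 45% versus 49%, with RR 1.09 and power about 88%; for f = 40% and 60% power is 91% and 99.6%. Step 3 therefore depends on the alert having the same effect on p among patients with and without prior use.

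**6. Drug stopping (assumed figures).** Suppose 30% are on the drug at randomization, 40% of them stop under usual care and 50% under the alert, and 3% of the other 70% start it later.

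- Whole-stay administration, both arms: 0.30 + 0.70 × 0.03 = 32.1%.
- Administration after randomization, allowing a short lag so that a stopped drug is not counted: 0.30 × 0.60 + 0.021 = 20.1% under usual care versus 0.30 × 0.50 + 0.021 = 17.1% under the alert, with power about 85%.

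On the whole-stay administration measure the effect of stopping disappears.

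**The case against.** The strongest reply is that post-AKI care was intended all along. A patient belongs to a study arm only after randomization, and naming the index hospitalization may serve only to exclude readmissions, which are the neighbouring item. The SAP's Intervention section describes provider education that covered "the rates of best practice completion after AKI has developed". A creatinine-monitoring item fixed at 100% would be pointless, which also suggests that nobody meant it. This makes the intent plausible, but the last quote describes teaching content and nothing here sets an endpoint window. A reader might infer that pre-randomization care was certainly counted. The documents do not show that; they show only that the stated window does not exclude it.

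A second reply concerns cessation. A reader might infer that stopping a drug cannot register at all. That is wrong for the protocol, which names cessation for NSAIDs and ACE inhibitors. The SAP list is introduced as what the practices included, so it need not be complete, and the SAP refers to a published design paper that is not available here. What stands is that cessation has no definition in the protocol and no place in the SAP list.

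Third, these are secondary outcomes, for which the SAP reports 95% confidence intervals and, safety outcomes apart, no p-values. Power is then only a proxy. Shrinkage of the estimate is the more direct measure, and it remains.

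Fourth, one might argue that an open-ended stay favours whichever arm stays longer. The protocol's Risks section says only that longer stays can be imagined and that the pilot did not show such behavior. Extra care during a stay prolonged by the alert is also arguably a genuine effect of it. That argument is not relied on here.

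**Conclusion.** The concern holds in this form: the plan does not start the care-practice window at randomization, and the one window it states takes in care that the alert could not affect. The consequence is dilution toward no difference. A reader might infer bias between the arms, but care before randomization is balanced in expectation, so that does not follow.

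The size is unknown. Under independence of prior and later use, the absolute difference is multiplied by (1 − f) whatever the base rate. The loss of power runs from severe at base rates of 20% to 30% to modest at 50%, and under the additive assumption in step 5 the absolute difference is not diluted at all. None of the tabulated figures estimates what happened in this trial, because base rates, pre-randomization shares and the scale of the 16% are all missing from the documents.

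Two results need no assumed rates: creatinine monitoring, read literally, cannot differ between arms; and a whole-stay administration measure cannot register the stopping of a drug already given. This deserves correction, in proportion to its place among the secondary endpoints.

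**What to change.** In both documents, count only orders or administrations time-stamped after randomization and within the index stay. A fixed cap, such as the day-14 limit of the primary outcome, is optional. If the analysis was already done this way, state it.

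For NSAIDs and for ACE inhibitors or angiotensin receptor blockers, report two measures: cessation among patients with an active order at randomization, with the period over which it is judged, and new starts among patients without one. Keep the whole-stay rates as descriptive. State the base rate, power and scale behind the 16%. This changes measurement only and touches no clinical rule.

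The cost is wording and re-programming. The SAP's Data Collection section says that laboratory data and medication exposures already come from the electronic record; that these carry usable order or administration times is assumed. Reported rates will be lower, and the cessation measures will rest on fewer patients: with 30% exposed, about 0.30 × 3,015 ≈ 905 per arm.
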